Patient Priorities Care requires the elicitation and documentation of patient health outcome goals and care preferences and the alignment of clinical care with goals and priorities to achieve patients' health outcome goals and reduce the burden of multi-morbidity. Participants will be enrolled in the Patient Priorities Care Program and speak with a trained health priorities facilitator to elicit their healthcare preferences and health outcome goals, which together constitute their health priorities. This information will be documented, entered into the EHR, and shared with the clinicians who will then use the Patient Priorities Care approach with patients to inform and guide treatment decisions. Patients will participate in the program and be followed for up to one year from the health priorities identification visit.

Sample

Patients: Potentially eligible participants for this project include Medicare beneficiaries (Traditional, Medicare Advantage, and dual eligible) 66 years or older who are patients of participating clinicians.

We assessed the power to detect clinically relevant differences in Patient-Reported Outcomes (PROs) and categories of healthcare utilization, both needed to measure value. We calculated minimal detectable differences for the primary PPC outcomes based on a sample size of 500 participants (250 PPC and 250 in UC) that assumed 80% power, a one-tailed alpha of 0.05, and an R-squared of 0.2 from other covariates. Assuming a standard deviation of 24.1 at pre-test and 17.6 at post-test and a correlation between measurement pairs of 0.55 (based on pilot data) allows us to detect a between-group difference in mean change in the TBQ score from pre-test to post-test of -4.6 points.³⁷ Comparing the PPC group to the UC care group, our sample permits us to detect an odds ratio of 1.7 with respect to discontinuing medications and an odds ratio of 0.52 with respect to having diagnostic tests ordered.³⁸

Inclusion/Exclusion Criteria

The evaluation of PPC in the clinical practice will take place as part of the patient's ongoing healthcare, and is minimal risk. Criteria for inclusion in the clinical program will be expansive in order to offer the opportunity for the largest number of reachable patients possible. All recruits will be those who are currently patients at Cleveland Clinic. Patient's meeting any of the exclusion criteria will not be approached by the Cleveland Clinic clinicians.

Inclusion Criteria:

1. Age 66 and older

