Clinical Procedures				Goal Facilitation Visit(s)	PPC Clinician Visit(s)	Goal Facilitator Follow up		
Research Procedures		Pre-Screening	Baseline Interview				Follow up interview	Follow up
	Week	Up to -7	-5 to 0	-6 to -1	0	2 to 6 (1-2wk after 1 st PCP)	34 to 52	Up to 52
	Month		-1	-1	0	1-2	8 – 12	12
Intervention arm	Consent		x				x	
	EHR data extraction		x					x
	Identification/ discussion of patient health priorities			x	x	x		

	Interview 
 • Demographics • 5-word recall* • PROMIS • CollaboRATE • Tx Burden questionnaire 		x					x	
	PCP visit			x					
Usual care arm	Interview 
 • Demographics • 5-word recall* • PROMIS • CollaboRATE • Tx Burden questionnaire 		x				x		
	PCP visit				x		x	x	
	EHR data extraction		x						x

*Baseline in-person interview only.

Patients meeting criteria within the Cleveland Clinic Lakewood Family Health Center (FHC) and Brunswick FHC patients who are scheduled to have visit during study period will be recruited using mail, or My Chart message about the project taking place. Lakewood FHC will be serving as intervention site and Brunswick FHC as usual care. Eligible and consented patients will participate in the program and be followed for up to one year from the goal elicitation visit. Primary physicians, and priorities facilitators (i.e. Geriatrician, MAs, Care Coordinators, Patient Liaison Program Coordinators, and Nurse practitioners) will undergo training and preparation to elicit and provide care aligned with health priorities. This training has been developed and tested during the Yale University pilot study of Patient Priorities care.

Pre-screening and Recruitment (Research procedure)

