A list of patients meeting above criteria will be generated by the methods described below, and provided to PCPs to obtain their permission to invite patients. PCPs may suggest removing any patients who may not be appropriate for the intervention at PCP's discretion. Research team will conduct a baseline interview after obtaining verbal consent from the patients. Priorities Facilitators will be notified to invite these patients to have their health priorities identified and their care aligned with these priorities. To maximize flexibility and align with current workflow, the invitation for priorities identification can be during a regular visit, by phone, by mail, or other means already used by the practices (e.g. same visit as invitation; part of annual wellness visit, etc.).

Project specific generated list: Each week, a scheduling system will provide an automated list of targeted patients with appointments 6 weeks later. Appointment types include in-person office visit, distance health, virtual, or telephone visit. This system is linked with EHR and widely used at our institution. Once target patients are identified and approved by the PCP, research personnel will contact via mail, or My Chart messaging to introduce the Patient Priorities Care program with an information sheet to explain the Patient Priorities Care process and ask them to contact the research team if they want to opt out. Opt-out patients will be recorded in the screening log to avoid contacting again for future recruitment.

Care providers referral: Care providers can make a referral if they have patients who could benefit from the Patient Priorities Care program, otherwise meet inclusion and exclusion criteria, and have regular visits in next few months. Care providers can discuss the program and provide information sheet to the potential participants. Clinician will notify the research team of the potential patients who have agreed to participate in the PPC. Research team will contact these potential participants to obtain consent to participate in Patient Priorities Care before asking any research questions. Care providers will also notify names of patients who decline to participate in order to avoid contacting the same patients again for future recruitment.

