Primary Care Coordination patients list: For patients enrolled through the Care Coordination program, research personnel will identify the individuals ahead of time and obtain permission from their PCPs. Research team will contact via mail, or My Chart messaging to introduce the Patient Priorities Care program with an information sheet to explain the Patient Priorities Care process and ask them to contact research team if they want to opt out. After excluding patients who opted out, research personnel will contact patients to obtain consent and conduct baseline interview. Because this project provides prioritized patients' list based on their existing Care Coordination patient list for the Coordinators to reach out, this process adds very little burden on Care Coordinator's part.

Usual care Group

Concurrent to the Patient Priorities Care implementation, we will begin to identify the usual care group which will include up to 250 patients. We will identify a sample similar to the intervention group, using the same inclusion/exclusion criteria and clinical judgment. The usual care group will be identified from Brunswick FHC patients.

The usual care group will be identified through the same electronic health record search and Care Coordination patient list described above, and PCPs will have the option of not including any of their patients for interview for usual care group.

The usual care group during the study period will receive a recruitment letter from their clinician

describing the research and interview. Patients will be able to opt-out if they do not wish to be contacted by contacting research team listed in the invitation letter. For patients who do not opt-out, a centralized, trained research personnel will contact candidates by phone to confirm eligibility and to obtain verbal consent for enrollment in the usual care arm which involves standard clinical care, data collection through an interview, and a medical record review.

Consent process

We will require a full waiver of consent and HIPAA authorization for the health care utilization data that will be used as part of the screening process and evaluation of the patient population. We will also request a waiver of signed consent and HIPAA authorization for participation of clinicians and patients in the research evaluation. It would be impractical to gain signed consent for this information, specifically for this population and the research involves minimal risk.

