Consent process will be conducted primarily over the phone by a trained project staff member. Patients will be notified via letter, My Chart message or phone that a CCF research personnel will be contacting them to conduct the interviews. A trained research coordinator will administer the qualitative survey. Participants in both intervention and usual care groups will receive \$10 for each research interview for a total reimbursement of up to \$20.

Baseline interview

Once potential patients are identified, research personnel will add participants' contact information into a secure electronic data collection system (REDCap) which the research team will also use to contact the participants to administer the interview. Up to 6 weeks prior to their next PCP appointment, selected patients will be contacted by phone or in-person to confirm consent to participate. Once eligibility is confirmed, research personnel conduct phone or in-person baseline interview whichever is preferred by the patient. Baseline interview could follow after Priorities Facilitators (Geriatrician, MA, Care coordinator, Patient Liaison Program Coordinators, Nurse Practitioners) completes priorities identification process. This can be done before or the day of the initial PCP visit to begin deciding treatment plans based on priorities. Contact information will be stored separately from interview and medical record data and destroyed once the follow-up interviews have been conducted and data collection and cleaning is complete.

Priorities Facilitators will help patients identify their health priorities, complete the health priorities template in EHR. Please note that similar process has been routinely done at the clinic as part of Care Coordinators' and Patient Liaison Program Coordinators' job (Appendix 1), and this project provides more structure in documentation and collaboration with other care providers involved.

PCPs will be asked to review the patients' health priorities at subsequent clinical follow up visits and update if necessary.

At the intervention site, we will identify site champions to develop continued buy-in from providers (e.g., staff meetings, individual meetings, case examples), obtain feedback, and notify the PI and research team of unanticipated problems.

Intervention (Clinical procedure)

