Follow up data collection will be two-fold: We'll conduct phone (or in-person) interview and ask the same questions except cognitive ability screening items at 8-10 months from the baseline; and we'll collect patient-level utilization and other clinical variables from EHR from 3 months prior to baseline date through up to 12 months after the baseline date.

Follow up interview: Approximately 9 months from the PCP visit, follow up interview will be conducted by phone or in-person. All patients who participated in the intervention will be contacted at 9 month (+/- 30 days protocol window) to complete follow up interview defined in the variable list. A week prior to follow up interview period, research personnel will send mail/My Chart message or call to remind participants of the follow up interview session. If participant does not respond to the follow up interview invitation by the 9th month, we will follow up with a letter with the interview form and self-addressed, stamped envelope enclosed. We will ask patients to fill the forms and send back by mail.

Post-Follow up interview: Research personnel will contact enrolled patients who completed follow up interview for missed question items from the follow up interview by calling messaging. If an enrolled participant does not respond to the Post-follow up interview invitation by the 12th month from baseline, we will follow up with MyChart message or a letter with the interview form and self-addressed, stamped envelope enclosed. We will ask patients to fill the forms and send back by MyChart message link or mail. This procedure only apply to enrolled patients who completed follow up interview but missed questions due to Redcap programing error reported on 7/15/2021 as Unanticipated Problem.

Data extraction: From 3 months prior to Baseline Interview through up to 1 year from the Baseline Interview, the following information will be ascertained from patients who gave consent: The number and types of chronic conditions (collected at Baseline only), medications, Healthcare activities defined as below, ACP (Advance Care Planning) tab use, and the Accountable Care Organization (ACO) survey as defined below.

Data Collection overview

In the 2 participating sites (Lakewood and Brunswick) the following information will be collected:

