The use of verbal permission is being requested. The research personnel performing the baseline interviews, the health priorities facilitator or the participating clinician will obtain verbal permission from patients who received Patient Priorities Care during the first encounter with patient priorities care. This will allow project staff to provide the pre/post qualitative and quantitative interviews/surveys over the phone but also obtain utilization data. These research personnel, priorities facilitators and clinicians are or will be trained in obtaining verbal permission.

The use of verbal permission will also ensure the safety of potential participants and be appropriate mode of communication during the COVID-19 pandemic.

For initial patient identification process, a waiver of HIPAA authorization is being requested to identify those participating in the clinical program. It would be impractical to gain consent from all the patients whose records will be viewed in order to identify appropriate individuals to invite to participate. These records are being viewed as part of ongoing clinical care, and the information will not be share with any personnel outside of CCF.

References

1. Chevarley, F.M. Expenditures by number of treated chronic condition, race/ethnicity, and age, 2012. Statistical Brief #485. Rockville, MD: Agency for Healthcare Research and Quality; 2015. http://meps.ahrq.gov/mepsweb/data_files/publications/st485/stat485.pdf. Accessed February 21, 2019.

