Potentially eligible participants include patients 65 years or older who are patients of participating clinicians. Criteria for identifying eligible persons from administrative or electronic health record (EHR) data include combinations of ≥ 3 chronic conditions; ≥ 10 medications; >1 hospitalization (or >10 days in the hospital); >2 ED visits over the past year; seen by ≥ 2 specialists over past year; receive any care coordination services. Exclusion criteria include hospice eligibility, advanced dementia or moderate to profound intellectual disabilities, not English speaking or nursing home residence. A list of patients meeting above criteria will be generated and provided to PCPs to obtain their permission to invite patients. PCPs may suggest removing any patients who may not be appropriate for the intervention.

Aims and objectives

Primary aim: Determine whether, post-intervention, patients enrolled in PPC report a greater improvement in achievement of desired activities, shared decision making and value and a greater reduction in levels of treatment burden from baseline than do those in the usual care cohort.

Secondary aim: Determine whether, post-intervention, patients enrolled in PPC achieve better alignment of care per Cleveland Clinic's ACO Survey Item

Outcomes

Outcome	Operationalization
Primary	
Treatment burden	Patient score on 'Treatment Burden Questionnaire' (TBQ, score range 0-150, Cronbach's alpha=0.90) [5]
Achievement of desired activities	Patient score on PROMIS Ability to Participate in Social Roles and Activities Short Form 6a (score range 6-30; Cronbach's alpha = 0.98) [6]
Nonhealthy days	Number of days in which patients dead or in hospital, emergency department, nursing home or undergoing ambulatory procedure requiring several hours for completion and recovery within 12 months following baseline interview [7], [8].
Shared decision making	Patient score on CollaboRATE tool (score 0-100, Cronbach α = 0.89; score range, 0-100 with higher score denoting greater perceived shared decision-making; dichotomized as 100 vs <100, with 100 representing a participant who reported the top score on all 3 items) [9]
Secondary	
Shared prescribing decision making	Response to Cleveland Clinic ACO survey item " When starting a new medication, did your provider ask what you thought was best for you? "

Populations and subgroups to be analyzed

None planned

Analyses

Propensity Weights

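### The protocol is inconsistent on whether PPC-arm entry and follow-up depend on enrolment or on receiving PPC, and the SAP defines no analysis population to settle it

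*Protocol*

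**What the plan says.** Some protocol text ties the PPC arm to receipt of the intervention:

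- Follow up data collection, Follow up interview: "All patients who participated in the intervention will be contacted at 9 month (+/- 30 days protocol window) to complete follow up interview". The phrase about participating is not defined, and the sentence gives no contact rule for usual care.
- Consent: research personnel, the facilitator or the clinician "will obtain verbal permission from patients who received Patient Priorities Care during the first encounter with patient priorities care". This permission also covers utilization data.
- Baseline interview: "Baseline interview could follow after Priorities Facilitators" have completed priorities identification.
- Study Design, Methods: "Patients will participate in the program and be followed for up to one year from the health priorities identification visit".

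Other text points to enrolment:

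- Procedures, after Table 1: "Eligible and consented patients will participate in the program and be followed for up to one year from the goal elicitation visit". The subject is consented patients, although the clock is still the elicitation visit.
- Pre-screening and Recruitment: consent and the baseline interview come first, and then "Priorities Facilitators will be notified to invite these patients to have their health priorities identified and their care aligned with these priorities".
- Study Design, Methods: arms are set by practice location.
- Follow up data collection: the interview is placed 8-10 months from baseline (and, in the next paragraph, about 9 months from the PCP visit). EHR data are taken from patients who consented.

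At the usual-care site, staff phone candidates "to obtain verbal consent for enrollment in the usual care arm which involves standard clinical care, data collection through an interview, and a medical record" (that is, a chart review). Table 1 schedules a follow-up interview for them.

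Under "Populations and subgroups to be analyzed" the SAP says only that none are planned. Both documents plan multiple imputation.

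**The concern.** Because consent normally precedes the facilitator's invitation, a PPC-site patient can enrol and never have a priorities visit. Neither document says whether that patient is interviewed at follow-up or how the patient is analysed. A usual-care patient cannot fall into this gap.

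If the receipt-based wording governs, TBQ, PROMIS and CollaboRATE are observed in PPC patients who completed an extra step and in usual-care patients who were not filtered. Completers may differ from non-completers in engagement and burden, so the arms could differ at follow-up with no effect of PPC.

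Where permission is first taken at the first PPC encounter, entry to the dataset itself depends on receipt. Nonhealthy days, taken from records, could then be affected as well.

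**Working it through.** **1. The two readings, by type of patient**

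| PPC-site patient | Receipt-based wording | Enrolment-based wording |
|---|---|---|
| Consented, had a priorities visit | Interviewed; EHR data | Interviewed; EHR data |
| Consented at baseline, no priorities visit | Not contacted; EHR data still available | Interviewed; EHR data |
| Would be asked only at the first PPC encounter, never attends | Not in the dataset | Asked earlier; in the dataset if consenting |

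The readings differ in the second and third rows. The usual-care arm has no equivalent of either row.

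**2. What the planned methods can repair**

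- Propensity weights balance baseline characteristics. They do not address selection on an event after enrolment, except through baseline variables related to it.
- Imputation can keep second-row patients. It removes the bias only if non-participation is uninformative given the imputation variables. The SAP lists no such variables and no sensitivity analysis.
- Third-row patients leave no record to impute.

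**3. The protocol's benchmark**

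Inputs (Protocol, Sample): SD 24.1 before and 17.6 after, correlation 0.55, 250 per arm, 80% power, one-tailed alpha 0.05.

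- SD of change = √(24.1² + 17.6² − 2 × 0.55 × 24.1 × 17.6) = √(580.81 + 309.76 − 466.58) = 20.59.
- Detectable difference = (1.645 + 0.842) × 20.59 × √(2/250) = 4.58, against the stated 4.6. It reproduces.
- This match leaves out the stated R-squared of 0.2; with it, one-tailed, the figure is 4.10.
- At the SAP's 125 per practice, on the same basis: (1.645 + 0.842) × 20.59 × √(2/125) = 6.48.

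**4. Size of the shift, on assumed inputs**

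The documents give no uptake rate and no completer difference. Assume a proportion p = 0.10 to 0.30 of enrolled PPC patients lack the visit, and that their follow-up TBQ is worse by d = 0.25 to 0.5 SD, with SD 17.6. The mean of completers differs from the mean of all enrolled by p × d × 17.6:

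- Low: 0.10 × 0.25 × 17.6 = 0.44 points.
- Middle: 0.20 × 0.5 × 17.6 = 1.76 points.
- High: 0.30 × 0.5 × 17.6 = 2.64 points.

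As a share of the detectable difference:

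- At 250 per arm: 0.44/4.6 = 10% to 2.64/4.6 = 57%.
- At 125 per arm: 0.44/6.48 = 7% to 2.64/6.48 = 41%.

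**5. Effect of baseline adjustment**

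The figures in step 4 are before covariate adjustment. If non-completers were worse by the same d at baseline, adjusting for baseline TBQ with correlation 0.55 would leave a fraction 1 − 0.55 = 0.45. That is 0.45 × 0.44 = 0.20 to 0.45 × 2.64 = 1.19 points. If they did not differ at baseline on TBQ or the other covariates, adjustment would remove none of it.

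**The case against.** The strongest reply is that participation here simply means enrolment. The protocol's referral paragraph speaks of consent to participate in PPC. The contact sentence cannot be an exhaustive rule, because usual care would then have no follow-up interview; yet Table 1 schedules one, and both groups are paid for two interviews. The Data Collection overview describes patient-reported outcomes at baseline and about 9 months at both sites, with no participation condition. A follow-up limit counted from the priorities visit caps duration and need not be an entry condition. The Consent section lists the baseline interviewers first among those who take permission. The SAP's statement that no populations are planned can mean that no restricted subset will be used.

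Much of this stands. A reader might infer that the comparison does select on receipt of PPC, that nothing brings lost patients back, and that every outcome is biased toward PPC. The documents do not support that. No passage excludes non-completers, several passages point to enrolment, and imputation is planned. EHR outcomes cover everyone who consented. The direction is not documented either: if less-burdened patients skip the visit, the bias reverses.

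The reply does not remove the inconsistency. The same section uses the word enrolled for the post-follow-up contact but a different term in the main contact rule. Table 1's usual-care row says nothing about non-completers within the PPC arm. Neither document says what happens to them.

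**Conclusion.** The point holds as an unresolved inconsistency with a real route to bias, not as a demonstrated selection rule. One set of protocol passages makes PPC permission, baseline timing and follow-up contact depend on receipt; another makes them depend on consent and site; the SAP does not choose.

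If the receipt-based wording was followed, interview outcomes are selected in one arm only. For patients first asked at a PPC encounter, record-based outcomes are too.

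The size and sign are unknown. The 0.4-2.6 TBQ points rest entirely on the assumed non-completion and completer difference, apply before covariate adjustment, and ignore weighting and imputation. Against 4.6 at 250 per arm, or about 6.5 at 125, that range runs from minor to large enough to affect interpretation.

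**What to change.** **Protocol.** State that all consented patients at both sites, whether or not a priorities visit took place, are contacted about 9 months from the baseline interview. Define enrolment in both arms as consent at a baseline interview held before priorities identification. Bring the Consent, Baseline interview and follow-up passages into line with this.

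**SAP.** Define the primary population as all consented patients, analysed by practice site at baseline. Keep PPC patients without a priorities visit, with EHR outcomes as observed and missing patient-reported outcomes imputed. Report how many there were, how many of them were interviewed at follow-up, and how many PPC patients were consented or interviewed only after priorities identification.

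**If follow-up is complete.** The SAP is dated 2024, refers to the reduced sample in the past tense, and the protocol mentions a follow-up interview error reported in July 2021. The contact rule may therefore no longer be changeable. The population definition and the counts still apply, and they show readers whether the problem arose.

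**Cost.** A few sentences, a flow count and, if still possible, some extra calls. The effect estimate is somewhat diluted. If PPC does nothing for patients without a visit, a 4.6-point effect in completers becomes 4.6 × 0.9 = 4.14 at 10% non-completion and 4.6 × 0.7 = 3.22 at 30%.
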